### **8.4.2 Efficacy/Pharmacokinetics/Pharmacodynamics Endpoints**

Secondary endpoints are presented below:

**Objective Response Rate (ORR):** is defined as the percentage of subjects who have achieved confirmed complete response (CR) or partial response (PR) according to RECIST v1.1 or PCWG2 as assessed by investigator radiologic review.

**Duration of Response (DOR):** is defined as the time interval between the date of the first confirmed response (CR/PR) (the response prior to confirmation) and the date of first documented disease progression based upon RECIST v1.1 or PCWG2 as assessed by investigator radiologic review.

**Disease Control Rate (DCR):** is defined as the percentage of subjects who have achieved stable disease or confirmed complete response (CR) or confirmed partial response (PR) according to RECIST v1.1 or PCWG2 as assessed by investigator radiologic review. Subjects with missing response will be considered not to have achieved disease control.

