#### **4.2.3.4 Efficacy Endpoints**

##### **4.2.3.4.1 Secondary Efficacy Endpoints: RECIST or PCWG -based Response Rate**

A secondary efficacy objective of this trial is to evaluate the anti-tumor activity of MK-8628 in subjects with selected advanced solid tumors (NMC, NSCLC, TNBC and CRPC). Secondary efficacy endpoints include (1) ORR, defined as the percentage of subjects who have achieved confirmed complete response (CR) or partial response (PR) according to Response Evaluation Criteria in Solid Tumors (RECIST) v1.1 (see Section 12.8) or Prostate Cancer Clinical Trials Working Group (PCWG2) (see Section 12.9), as assessed by investigator radiologic review; (2) DOR, defined as the time from first documented evidence of CR or PR until disease progression or death due to any cause, whichever occurs first; and (3) DCR, defined as the percentage of subjects who have achieved stable disease or confirmed complete response (CR) or confirmed partial response (PR) according to RECIST v1.1 or PCWG2, by the investigator review

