### **7.1.2.6 Tumor Imaging and/or Bone Scan**

#### **7.1.2.6.1 CT, MRI and/or Chest X-Ray**

For tumor evaluation, a CT, MRI and/or chest X-ray (posterior-anterior and lateral) will be performed every 6 weeks ( $\pm$  3 days) by calendar date starting from Cycle 1 Day 1 (not adjusted for cycle or treatment days). These assessments will be performed on approximately Day 1 of every 2nd cycle (C3, C5, C7, etc.), as clinically indicated by the subjects diagnosis. Scans used may be requested for central review. Effort should be made to maintain the same imaging modality throughout the study.

In subjects who discontinue study therapy without documented disease progression, every effort should be made to continue monitoring their disease status by radiologic imaging every 6 weeks  $\pm$ 3 days until (1) the start of new anti-cancer treatment, (2) documented disease progression, (3) death, or (4) the end of the study, whichever occurs first. If subjects have stable disease, partial response, or complete response, they should continue on this every 6 weeks  $\pm$ 3 days assessment schedule. The timing for these assessments should continue the same imaging schedule from the treatment phase. Imaging should occur at any time where there is clinical suspicion of progression.

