#### **7.1.2.6.3 Assessment of Disease**

Tumor lesions will be assessed throughout the study according to RECIST criteria (version 1.1) [101] (see Section 12.8). Any tumor shrinkage, in terms of percentage of tumor regression, will be reported even if it does not meet RECIST criteria for response. While RECIST criteria (version 1.1) do not require confirmation of objective response in clinical studies where response rate is not the study primary endpoint, as a convincing proof-of-concept of antitumor activity, efforts should be made to confirm objective response at least 4 weeks apart.

For CRPC subjects, PSA response rates will be measured according to the PCWG2 criteria [102] (see Section 12.9). RECIST v1.1 is used to assess soft tissue disease [101]. Progression

of bone disease is defined using PCWG2 criteria, namely a confirmed increase of at least two new lesions on a bone scan.

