#### **7.1.5.4 Post-Treatment**

Visit requirements are outlined in Section 6.0 - Trial Flow Chart. Specific procedure-related details are provided above in Section 7.1 - Trial Procedures

After the last treatment administration, subjects will be followed up for safety for 30 days and then until resolution of any AEs for which a relationship to MK-8628 cannot definitely be excluded (or categorized as sequelae). A visit will be performed 30 days (+5 days) after the last MK-8628 intake.

In subjects who discontinue study therapy without documented disease progression, every effort should be made to continue monitoring their disease status by radiologic imaging\* every 6 weeks ( $\pm 3$  days) until (1) the start of new anti-cancer treatment, (2) documented disease progression, (3) death, or (4) the end of the study, whichever occurs first. \*Note: This includes bone scans for CRPC subjects every 12 weeks ( $\pm 3$  days). If subjects have stable disease, partial response, or complete response, they should continue on this assessment schedule. The timing for these assessments should continue the same imaging schedule from the treatment phase. Imaging, and if applicable, bone scans, should occur at any time where there is clinical suspicion of progression.

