## **8.6 Statistical Methods**

This section describes the statistical methods that address the primary and secondary objectives. Methods related to exploratory endpoints will be described in the supplemental SAP. Data will be presented by dose level, and where appropriate by indication. No imputations for missing data will be made.

Pharmacokinetics and pharmacodynamics will be analyzed and reported separately.

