### **8.6.1 Statistical Methods for Efficacy Analyses**

ORR and DCR with 95% confidence intervals will be estimated using Exact method based on binomial distribution (Clopper-Pearson interval).

DOR will be estimated by Kaplan-Meier method.

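### SAP section 8.4.2 ends duration of response at progression only, while section 4.2.3.4.1 also counts death, and section 8.6.1 does not say how deaths enter the Kaplan-Meier estimate

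*Combined protocol and SAP*

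**What the plan says.** DOR stands with ORR and DCR among the secondary efficacy endpoints (sections 3.2, 4.2.3.4.1, 8.1 and 8.4.2). Section 4.2.3.4.1 defines it as "the time from first documented evidence of CR or PR until disease progression or death due to any cause, whichever occurs first".

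Section 8.4.2 defines it again. The start is "the date of the first confirmed response (CR/PR) (the response prior to confirmation", that is, the first documentation of a response that is later confirmed. The end is given as "and the date of first documented disease progression based upon RECIST v1.1 or PCWG2 as assessed by investigator radiologic review". Death does not appear.

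On method, section 8.6.1 says only: "DOR will be estimated by Kaplan-Meier method". Section 8.6 adds: "Methods related to exploratory endpoints will be described in the supplemental SAP". That sentence does not reach DOR, which is secondary; the same section says that it covers the methods for the primary and secondary objectives. Its statement that missing data are not imputed is not a censoring rule. By contrast, PFS in section 4.2.3.4.2 counts death from any cause as an event, and DCR in section 8.4.2 has its own rule for missing responses.

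**The concern.** A Kaplan-Meier estimate needs a defined event and a rule for everyone who does not have it. Under 4.2.3.4.1 a responder who dies without documented progression has had the event. Under 8.4.2 that responder has not, and would ordinarily be censored. Censoring treats the dead responder as if still open to progression at the same rate as the survivors, which makes responses look more durable.

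The situation can arise in this trial. Section 4.1.1.1 cites a median survival of 6.7 months in NMC, and up to 30 NMC subjects may enter Part B. Section 4.1.3 reports responses in 2 of 5 NMC subjects at 80 mg QD continuous dosing in the earlier solid-tumor study. Imaging is every 6 weeks, and section 12.8.3 foresees subjects stopping for clinical deterioration before progression is shown objectively. The documents give no rate for deaths of this kind.

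At stake is the description of how long responses last. The trial is open-label, so a choice between the two definitions could be made after the responders' outcomes are known.

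**Working it through.** **1. Figure to reproduce.** There is none. The plan states no expected DOR, number of responders or precision for DOR; Table 13 covers only the DLT rate and ORR.

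**2. The two definitions, case by case, for the same start date.**

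| Responder's course | 4.2.3.4.1 | 8.4.2 |
|---|---|---|
| Progression documented first | Event | Event, same date |
| Death without documented progression | Event at death | Not an event; ordinarily censored |
| Neither | Censored, date not stated | Censored, date not stated |

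Only the second row separates them.

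**3. Direction.** The Kaplan-Meier curve is the product, over event times, of (1 − events / number at risk). If the responder leaves the risk set at the date of death under either definition, the numbers at risk are identical. The only change is that the factor at each such death becomes 1 instead of something below 1. The 8.4.2 curve is therefore never below the 4.2.3.4.1 curve, and its median is equal or longer. If deaths were censored at the last scan instead, the responder would leave the risk set earlier and this ordering would no longer be guaranteed in every sample.

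**4. Size, as illustration only.** Assume exponential times and let d be the share of DOR-ending events that are deaths without documented progression. With total hazard λ, the median counting deaths is ln 2 / λ. With deaths censored, only the progression hazard (1 − d)λ remains, so the median is ln 2 / [(1 − d)λ]. The ratio is 1 / (1 − d). The 6.0-month reference median is also an assumption.

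| Assumed d | Ratio 1/(1 − d) | A 6.0-month median becomes |
|---|---|---|
| 0% | 1.00 | 6.0 |
| 10% | 1/0.9 = 1.11 | 6.7 |
| 20% | 1/0.8 = 1.25 | 7.5 |
| 30% | 1/0.7 = 1.43 | 8.6 |

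**5. Few responders.** Assume five responders with events at 2, 4, 6, 8 and 10 months, and take the median as the first time the curve is at or below 0.5.

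- All five count as events: 0.8, 0.6, 0.4, so the median is 6.
- First is a censored death: 3/4 = 0.75, then 0.75 × 2/3 = 0.50 at 6 months; median 6.
- Second is a censored death: 0.8, then 0.8 × 2/3 = 0.53 at 6 months, then 0.53 × 1/2 = 0.27 at 8 months; median 8.
- Third is a censored death: 0.8, 0.6, then 0.6 × 1/2 = 0.30 at 8 months; median 8.
- Fourth or fifth is a censored death: median still 6.

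The median moves only if the second or third event is such a death. If each event is one independently with probability d, the chance is 1 − (1 − d)²: 19%, 36% and 51% for d = 10%, 20% and 30%. In many small samples the two definitions would give the same median.

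**The case against.** The strongest reply is that little hangs on this. The trial is an estimation study with no hypotheses (sections 8.3 and 8.8). Results are shown by dose level and, where appropriate, by indication, so a cell may hold very few responders and a DOR median would be imprecise under either definition. Section 8.0 also lets changes to non-confirmatory analyses be recorded in a supplemental SAP before database lock, so the sponsor arguably has a route that needs no protocol amendment. All of this stands as a limit on severity. It does not remove the conflict: section 8.0 is a route to a rule and contains none, and nothing says which definition prevails.

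Three stronger readings are tempting.

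- A reader might infer that the start dates conflict as well, because the DOR clause in 4.2.3.4.1 does not mention confirmation and section 7.1.2.6.3 says only that "efforts should be made to confirm objective response at least 4 weeks apart". The documents do not support a material conflict. The parenthesis in 8.4.2 takes the start back to the response before confirmation, so an ordinary confirmed responder has the same start date in both sections. The 6-weekly scans already meet the 4-week interval. The dates part only in an unusual sequence, such as an unconfirmed response followed later by a confirmed one, or if unconfirmed responders were included under 4.2.3.4.1.
- A reader might infer that dose selection is biased. Section 5.2.1.5 makes the DLT rate the main driver and treats early efficacy signal as supportive, and the documents do not say whether DOR forms part of that signal.
- A reader might treat the missing censoring rule as an error in its own right. For responders with neither event it is missing detail, which the sponsor can supply by any stated convention.

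**Conclusion.** The point holds as a contradiction between two current definitions of a secondary endpoint. As written, the SAP definition would ordinarily censor deaths without documented progression. For the same start date and censoring at death, it yields a Kaplan-Meier DOR equal to or longer than the protocol definition.

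The size cannot be determined from the documents. It is zero if no responder dies without documented progression. The 1.11 to 1.43 inflation of the median rests on exponential times and an assumed 10% to 30% share of such deaths, and it describes large samples. The DLT endpoint and the sample size are untouched. The correction should be made, but the trial's primary purpose does not depend on it.

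**What to change.** - **Section 8.4.2:** end DOR at the earlier of first documented progression and death from any cause. This matches 4.2.3.4.1 and the PFS event in 4.2.3.4.2.
- **Section 8.6.1:** state that death without documented progression is an event, and how responders with neither event are censored, including those who start new anti-cancer therapy, at which point post-treatment imaging follow-up stops. The exact convention is the sponsor's choice; it should be written down before responders' outcomes are reviewed.
- **Wording note only:** use the 8.4.2 start date, the first documentation of the response that is later confirmed, in both sections.

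The cost is a few sentences. No new data are needed. Section 7.1.5.4 already says "In subjects who discontinue study therapy without documented disease progression, every effort should be made to continue monitoring their disease status", and section 7.1.2.6.1 continues imaging until (1) "the start of new anti-cancer treatment, (2) documented disease progression, (3) death, or (4) the end of the study, whichever occurs first". The downside for the sponsor is that the reported DOR may be slightly less favourable.

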#### **Pharmacokinetics**

Plasma parameters of MK-8628 as appropriate and according to analyses performed (non-compartmental or nonlinear mixed effect modelling) (see Section 4.2.3.2).

#### **Pharmacodynamics**

Incidence and severity of AEs along with PK parameters will be analyzed in relation to the most pertinent biomarker(s), if any (see Section 4.2.3.3).

## **8.5 Analysis Populations**

### **8.5.1 Efficacy Analysis Populations**

Treatment **Full Analysis Set (FAS)**, also known as **evaluable for efficacy**: subjects who receive at least one dose of study drug.

### **8.5.2 Safety Analysis Populations**

**DLT Evaluable population**: subjects who receive at least 85% of the planned dose of study drug (18 days) or experience DLT during the first 21-day cycle.

The **All Subjects as Treated (ASaT)** population, also known as **treated population**, consisting of subjects who receive at least one dose of study drug, will be used for the analysis of all other safety data in this study.

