#### **5.2.1.2 Dose Escalation (Part A)**

A twice daily (BID) dose escalation will be performed using a 6+8 two-stage design with continuous DLT rate monitoring via a modified toxicity probability index (mTPI) (Ji design), targeting a maximum 25% DLT rate [1].

Starting from 20 mg BID, up to three planned dose levels may be evaluated: 20 mg BID, 30 mg BID 40 mg BID (all continuous daily). See [Table 4](#) and [Table 5](#) for the dose escalation scheme.

Table 4: Dose Escalation Scheme

Dose Level (DL)	MK-8628 (mg/dose)	Outcome (#DLT/#Subjects)* / Actions to be taken
	BID Regimen (continuous)	
DL 1	20	At each DL: - Escalate/de-escalate per DLT rate observed using mTPI Table ( Table 5 )
DL 2	30	
DL 3	40	

\* Evaluated during the first 21 days of treatment

Table 5: Modified Toxicity Probability Interval (mTPI) Design

Number of toxicities	Number of subjects treated at current dose								
	6	7	8	9	10	11	12	13	14
0	E	E	E	E	E	E	E	E	E
1	S	E	E	E	E	E	E	E	E
2	S	S	S	S	S	S	S	S	E
3	D	S	S	S	S	S	S	S	S
4	DU	DU	DU	D	S	S	S	S	S
5	DU	DU	DU	DU	DU	D	S	S	S
6	DU	DU	DU	DU	DU	DU	DU	DU	D
7		DU	DU	DU	DU	DU	DU	DU	DU
8			DU	DU	DU	DU	DU	DU	DU
9				DU	DU	DU	DU	DU	DU
10					DU	DU	DU	DU	DU
11						DU	DU	DU	DU
12							DU	DU	DU
13								DU	DU
14									DU

E = Escalate to the next higher dose  
S = Stay at the current dose  
D = De-escalate to the next lower dose  
DU = The current dose is unacceptably toxic  
Target toxicity rate = 25%

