Subjects may be enrolled continuously, such that the number of subjects who are enrolled but are not yet fully evaluable for DLT assessment may not exceed the number of remaining subjects who are at risk of developing a DLT before the dose would be considered unacceptably toxic. If 0 out of the first 6 subjects in a given dose level develop a DLT, then the dose can escalate to the next level without further expansion. If 3 subjects out of the first 6 subjects develop a DLT, the dose will be de-escalated to the next lower dose level. If  $\geq 4$  out of the first 6 subjects develop a DLT, this indicates an unacceptable toxicity. If 1 to 2 out of the first 6 subjects of a given dose level develop a DLT, expand the current dose level according to [Table 5](#) by continuing enrollment as follows. As stated above, the number of subjects who are enrolled at that dose but are not yet fully evaluable for DLT assessment may not exceed the number of remaining subjects who are at risk of developing a DLT before the dose would be considered unacceptably toxic (denoted as DU in [Table 5](#)). For example, if 2/7 subjects have experienced a DLT at a given dose level, no more than an additional 3 subjects should be enrolled at this dose level until additional DLT data are available. This is because this dose level would be considered unacceptably toxic if all 3 of the additional subjects experience a DLT (i.e., 5/10 subjects with DLT in [Table 5](#)). To find out how many more subjects can be enrolled, one can count steps in diagonal direction (down and to the right) from the cell (7 subjects, 2 toxicities) to the first cell marked DU.

De-escalation (D) or unacceptable (DU) at the starting dose level (DL1) indicates stopping of the trial. Escalation (E) at the highest dose level (DL3) indicates staying at that level. Note that while 25% has been the target toxicity rate used to generate the guidelines in [Table 5](#), the observed rate of subjects with DLT at the RP2D may be slightly above or below 25%.

Subjects not evaluable for DLT (i.e. receiving less than 85% of the intended cumulative dose in Cycle 1 for any reason other than toxicity; <18 days of treatment) and who do not experience DLT will be replaced.

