### 5.2.1.4 Dose Limiting Toxicity

For the dose escalation part of this study (Part A), a DLT is defined as any of the following toxicities occurring during the first cycle of treatment (21 days) for each dose level. See Section 5.9 for rules on replacement of subjects in the DLT period.

The occurrence of any of the following toxicities during Cycle 1, **if assessed by the investigator to be possibly, probably or definitely related to MK-8628**, will be considered a DLT:

Hematologic toxicity

- Grade 4 hematologic toxicity lasting  $\geq 7$  days, except thrombocytopenia
  - Grade 4 thrombocytopenia of any duration
  - Grade 3 thrombocytopenia is a DLT if associated with bleeding
- Febrile neutropenia Grade 3 or Grade 4

Non-hematologic toxicity

- Grade 4 non-hematologic toxicity (not laboratory)
- Grade 3 non-hematologic toxicity (not laboratory) lasting  $> 3$  days despite optimal supportive care. Grade 3 nausea, vomiting or diarrhea will be considered a DLT if lasting more than 3 days despite optimal supportive care.
- Any Grade 3 or 4 non-hematologic laboratory abnormality, if:
  - medical intervention is required, or
  - the abnormality leads to hospitalization, or
  - the abnormality persists for  $> 1$  week
- Any of the following liver test abnormalities are observed (see also Section 12.7):
  - ALT or AST  $> 8X$  ULN
  - ALT or AST  $> 5X$  ULN for more than 2 weeks
  - ALT or AST  $> 3X$  ULN **AND** (total bilirubin  $> 2X$  ULN **OR** INR  $> 1.5$ )
  - ALT or AST  $> 3X$  ULN with the appearance of fatigue, nausea, vomiting, right upper quadrant pain or tenderness, fever, rash and/or eosinophilia ( $> 5\%$ ), unless the investigator assesses the rash or fatigue to be related to MK-8628 and not related to liver impairment, with Sponsor's agreement

Other

- Any drug-related AE which caused the subject to discontinue treatment during Cycle 1
- Any study drug-related toxicity resulting in a subject missing  $\geq 20\%$  of planned doses during Cycle 1.
- Any treatment-related toxicity which causes a greater than 2 week delay in initiation of Cycle 2.
- Grade 5 toxicity

DLTs must be reported within 24 hours to the Sponsor as Events of Clinical Interest (see Section 7.2.3.2). If the event also meets the criteria for seriousness, follow the reporting guidelines for Serious Adverse Events (SAEs) outlined in Section 7.2.3.1.

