Note: Exception to be treated similar to Grade 1 toxicity 
 
• Grade 2 alopecia
 
• Grade 2 fatigue
 
	Any intolerable G2 non-hematologic toxicity lasting >7 days with or without dose reduction	Consider holding for persistent symptoms	Toxicity resolves to Grade 0-1 or baseline	Clinical AE resolves within 2 weeks: treat at same dose and schedule  Clinical AE does not resolve within 2 weeks: may consider resuming treatment at next lower dose level (Table 8)	Dose is interrupted for > 2 weeks.
	3, 4  Unless not optimally treated with supportive care (e.g. Grade 3 vomiting not adequately treated according to anti-emetic standard of care)	Yes	Toxicity resolves to Grade 0-1 or baseline	Resume treatment at next lower dose level (Table 8)	Toxicity does not resolve within 2 weeks of last dose. Permanent discontinuation should be considered for any severe or life-threatening event

After recovery from toxicity, treatment will be resumed at the next lower dose level (Table 8). For subjects treated at DL1 (20 mg BID), 10 mg BID will be evaluated.

Table 8: MK-8628 Dose and Schedule Modifications

Dose Level (DL)	Initial Dose	1st Modification
DL 1	20 mg BID continuous	10 mg BID continuous
DL 2	30 mg BID continuous	20 mg BID continuous
DL 3	40 mg BID continuous	30 mg BID continuous

Note: Dose modification for 10 mg BID continuous will only include dose interruption and no further reduction is allowed.

For subjects enrolled in Part B of the study (NMC Cohort), the same guidelines for dose modifications should be followed.

No more than one dose reduction should be implemented unless the investigator thinks it in the subject's best interests to pursue study treatment with further dose reduction (additional dose reduction by one dose level), with the Sponsor's agreement.

Dosing interruption for > 2 weeks due to toxicity will lead to definitive study treatment discontinuation, unless the investigator thinks it in the subject's best interests to pursue study treatment, with the Sponsor's agreement.

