### **5.9 Subject Replacement Strategy**

Subjects not evaluable for DLT (i.e. receiving less than 85% of the intended cumulative dose in Cycle 1 for any reason other than toxicity; <18 days of treatment) and who do not experience DLT will be replaced.

A subject who discontinues from the trial for any other reason will not be replaced.

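### The DLT Evaluable population in 8.5.2 lacks the toxicity exception of 5.2.1.2 and 5.9, so a subject under-dosed because of a non-DLT toxicity is not replaced yet drops out of the reported DLT rate

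*Combined protocol and SAP*

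**What the plan says.** Section 8.5.2 defines the DLT Evaluable population as "subjects who receive at least 85% of the planned dose of study drug (18 days) or experience DLT during the first 21-day cycle". The other safety population in that section, All Subjects as Treated, "will be used for the analysis of all other safety data in this study". The DLT rate, which is the primary endpoint (8.1, 8.4.1), is therefore left to the DLT Evaluable population. Section 8.6.2 reports it as a count, a percentage and an 80% credible interval from a Beta(1,1) prior.

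Section 5.2.1.2 describes a subject who is not evaluable for DLT as one "receiving less than 85% of the intended cumulative dose in Cycle 1 for any reason other than toxicity", adds a gloss of fewer than 18 days of treatment, and replaces that subject if there was no DLT. Section 5.9 repeats the rule and says that subjects who discontinue for other reasons are not replaced. The columns of Table 5 are headed "Number of subjects treated at current dose".

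Two DLT criteria in 5.2.1.4 bound the group at issue. One is "Any study drug-related toxicity resulting in a subject missing" 20% or more of planned Cycle 1 doses. The other is any drug-related event that makes the subject stop treatment in Cycle 1.

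**The concern.** The rule that moves the dose and the rate that is reported for that dose should rest on the same subjects. As worded, they can differ by those who needed a hold or a dose cut for toxicity without meeting a DLT criterion. One dose level could then have two DLT rates. Section 5.2.1.5 gives weight to the highest dose level with a rate below 25% but does not name the denominator. Section 8.7 reviews subjects evaluable for DLT without saying which definition applies. With 6 to 14 subjects per dose level, a single subject visibly changes the rate. If the conflict is not settled in advance, the denominator has to be chosen after the data are seen.

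**Working it through.** **Inputs.** 21-day cycle, twice-daily dosing (2.1): 2 × 21 = 42 planned doses. Evaluability at 85% (5.2.1.2, 5.9, 8.5.2). Missed-dose DLT at 20% or more (5.2.1.4). Restart at the next lower dose level (Tables 7 and 8). Assumption: held doses count as missed within Days 1 to 21. Footnote q of the flow chart moves visits and assessments to the dosing calendar, but if held doses were merely deferred, a hold could never trigger the 20% rule.

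**1. Reproducing the plan's interval.** The shortest 80% interval of Beta(x+1, n−x+1) matches all 11 rows of Table 13; for 3/14 it gives 0.102 to 0.367, as printed. Equal-tailed limits (0.122 to 0.393 for 3/14) do not match. The shortest interval is used below.

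**2. The definitions side by side, for a subject without a DLT.**

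| Reason for falling below 85% | 5.2.1.2 and 5.9 | 8.5.2 |
|---|---|---|
| Not toxicity | not evaluable, replaced | excluded |
| Toxicity that is not a DLT | not replaced | excluded |

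The second row is the conflict, and no other section resolves it. That the subject stays in the Table 5 count is inferred from the replacement rule and the column heading; no sentence says so.

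**3. Counting doses.** 0.85 × 42 = 35.7, so 36 doses are needed. 0.20 × 42 = 8.4, so 9 missed doses for drug-related toxicity make a DLT.

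| Missed | Received | 85% reached | Missed-dose DLT |
|---|---|---|---|
| 6 | 36/42 = 85.7% | yes | no |
| 7 | 35/42 = 83.3% | no | no |
| 8 | 34/42 = 81.0% | no | no |
| 9 | 33/42 = 78.6% | no | yes |

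Seven or eight missed doses meet neither rule. If toxicity in 5.2.1.2 also covers events judged unrelated to the drug, the missed-dose DLT does not cap the shortfall for those events.

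**4. Counting days with any dose.** A continuous 7-dose hold removes three full days and leaves 18 treated days, whether it starts in the morning or the evening. An 8-dose hold starting in the evening also leaves 18. Only an 8-dose hold starting in the morning removes four full days and leaves 17.

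**5. Two routes into the group.**
- "Grade 3 non-hematologic toxicity (not laboratory) lasting" exactly 3 days is not a DLT, because the criterion needs more than 3. Table 7 nevertheless requires a hold until Grade 0-1 or baseline. One further day at Grade 2 makes a four-day hold, which is 8 doses.
- Grade 3 thrombocytopenia lasting more than 7 days without bleeding is not a DLT here, but Table 7 requires a hold. A hold from the Day 18 blood count to Day 21 misses 4 × 2 = 8 doses. The earlier once-daily solid-tumor study saw two prolonged Grade 3 thrombocytopenias among 16 subjects at 80 mg continuous (4.1.3), so the toxicity is plausible, though this timing may be rare.

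**6. Counting mg.** Take a three-day hold from Day 8 (14 full doses, 6 held) and then 22 doses at the next lower level, r times the original. The share of planned mg is (14 + 22r)/42:
- 40 to 30 mg, r = 0.75: 30.5/42 = 72.6%
- 30 to 20 mg, r = 0.667: 28.67/42 = 68.3%
- 20 to 10 mg, r = 0.50: 25/42 = 59.5%

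Each subject has 18 treated days. Section 8.5.2 keeps them if read in days and drops them if read in mg. Section 5.2.1.2 does not replace them on either count, because the cause is toxicity.

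**7. Effect on the reported rate, one such subject removed.**
- 2/9 = 22.2% (80% interval 0.089 to 0.413) becomes 2/8 = 25.0% (0.102 to 0.454).
- 3/14 = 21.4% (0.102 to 0.367) becomes 3/13 = 23.1% (0.111 to 0.391).

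The numerator never changes, so x/(n−1) cannot be below x/n.

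**The case against.** The DLT rules already absorb most toxicity-driven shortfalls: 20% of doses missed, or a drug-related stop in Cycle 1, is itself a DLT and puts the subject in both sets. The remainder is narrow, depends on an unstated counting convention, and may be empty. If the 18-day gloss in 5.2.1.2 and 5.9 is read as a stand-alone test, the missed-dose part of the gap closes altogether; the dose-reduction part remains under a mg reading of 8.5.2. The direction is also conservative. All of this stands and limits the size of the point. It does not remove the difference in wording.

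Three stronger readings are tempting and are not supported.
- A reader might infer that Table 5 decisions, or the chance of escalating, would change. Nothing says that Table 5 uses the 8.5.2 count. On the reading adopted here it keeps the 5.2.1.2 count, and only the reported rate moves.
- A reader might infer that 5.2.1.2 measures dose while 8.5.2 measures days. Both pair 85% with 18 days. They share one ambiguity about what is counted after a dose reduction.
- A reader might treat 2/8 = 25.0% as failing a limit. Section 5.2.1.2 allows the observed rate at the recommended dose to lie slightly above or below 25%, and 5.2.1.5 makes the choice multi-faceted and aimed at a range.

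**Conclusion.** The concern holds as an inconsistency of definition with a small, conservative effect. Following the plan exactly, a subject below 85% because of a non-DLT toxicity is neither replaced nor included in the primary DLT rate. Each such subject lowers the denominator by one, which moves the rate by 1.6 percentage points at 3/14 (21.4% to 23.1%, from unrounded rates) and 2.8 points at 2/9 (22.2% to 25.0%).

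This rests on counting held doses as missed within Days 1 to 21, on the inference that unreplaced subjects stay in the Table 5 count, and on not reading the 18-day gloss as a separate test. The documents do not say how many such subjects to expect. Nor do they support a reading that toxicity is hidden: 8.5.2 removes only subjects without a DLT, so it can raise the reported rate and never lower it.

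**What to change.** Reword 8.5.2 along these lines:

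> DLT Evaluable population: subjects who have a DLT in Cycle 1, or reach 85% of planned Cycle 1 treatment, or receive less than 85% because of study-drug-related toxicity.

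State that this one population serves Table 5, the 8.7 reviews and the DLT rate in 8.6.2. Use the same study-drug-related qualifier in 5.2.1.2 and 5.9, which now say only toxicity; otherwise a shortfall from an unrelated event would still be handled in two ways. State once, for all three sections, whether 85% is counted in doses, days or mg after a dose reduction. Footnote, for each dose level, the number of subjects below 85% because of toxicity without a DLT. If the sponsor would rather exclude these subjects, changing 5.2.1.2 and 5.9 to match 8.5.2 also resolves the conflict.

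The cost is a few words in three sections and one footnote. Dosing records and event dates are already collected, and Table 5 is unchanged. The downside is that subjects with shortened exposure, who had less chance to show a later DLT in Cycle 1, stay in the denominator. The reported rate is then slightly lower than under 8.5.2 as worded (3/14 against 3/13), and the footnote makes that visible.
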